### SpHb :

#### Primary objectives

1. Determine diagnostic performance characteristics of SpHb for detecting anemia (Sensitivity, Specificity, False Positive and False Negative) compared to reference hemoglobin measurement by the hospital laboratory, based on WHO criteria for anemia. For comparison, total Hb determined by blood gas analyzer will also be measured and used only related to research. This value will be not recorded in the medical record and will be kept blinded to clinical care team. This will be completed if sufficient number of participants with anemia are enrolled during the study period. (If not, a separate study related to this objective will be designed)
2. Determine utility of SpHb for screening purposes
  - a. Establish threshold of SpHb that best predicts the clinical outcome of “acute treatment of anemia”, defined as: blood transfusion, admission to hospital for further workup of anemia, or admission to operating room

---

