# A Multi-Center Study on the Utility of Non-invasive Carboxyhemoglobin and Total Hemoglobin Measurement in Emergency Department Patients

## SUNE0002 version 3

---

- b. The threshold of SpHb will be determined by receiver operating curve analysis of the pooled results from the first set of 500 subjects for each institution.
- c. Validate the SpHb threshold that predicts the outcome of “acute treatment of anemia” using a second set of subjects of 500 subjects from each institution.

Secondary objectives:

1. Measure extent of agreement between SpHb and total Hb determined by central hospital laboratory. Total Hb determined by blood gas analyzer will also be compared to the central laboratory measurement.
2. Survey the provider to determine the impact of the screening test. Providers will be asked: Did SpHb screening expedite care of patients? Did SpHb screening identify occult anemia?

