### 5 SUBJECT SELECTION AND WITHDRAWAL

#### 5.1 Number of Subjects

At least 3000 subjects across three sites may be enrolled onto this study. We expect to enroll approximately 1000 subjects at each site. This sample size is based on previous experience that has have demonstrated: 1) Occult toxicity occurs in approximately 1-3/10,000 ED visits. 2) Higher numbers of CO, needed to determine extent of agreement between non-invasive and laboratory measurements, are infrequent.

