### 5.4 Study Timelines

Subject participation in this study is not expected to delay any care or prolong their stay in the ED. The study will be conducted approximately between October 1, 2016 and December 31, 2018. We anticipate enrolling an average of 10 patients a day.

**Subject Recruitment** Patients may be screened at triage with FDA approved oximeter devices as part of standard of care procedures. The results of this screening will be recorded in the chart if performed, by clinical staff as per routine procedure.

A convenience sample of patients aged 1 year and up presenting to the emergency department for any complaint and who have received or will receive a blood test for CBC or an IV catheter during their care (determined by their care provider independently) or will be approached by trained research staff for evaluation for enrollment in the study.

We will also approach patients with known CO exposure or who have anemia to enroll them in this study. The attending emergency physician will conduct usual clinical care; research staff will seek to obtain informed consent for this part of the study.

Research staff will also be notified of any patient presenting to the emergency department with suspected CO exposure (e.g. rescued from fire), toxicity or anemia, or patients with signs and symptoms of CO toxicity (unexplained headache, nausea, vomiting, dizziness or lightheadedness, syncope, neurological deficits, shortness of breath). The treating provider will be notified if the patient has agreed to participate. If the clinician determines an IV is necessary, these patients will also be eligible for inclusion in the study.

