# A Multi-Center Study on the Utility of Non-invasive Carboxyhemoglobin and Total Hemoglobin Measurement in Emergency Department Patients

## SUNE0002 version 3

---

recorded on the case report forms (CRF). Demographic information, height, weight, gender, age, skin color, vital signs (heart rate, blood pressure, respiratory rate, pulse oximetry), presence or absence of jaundice, smoking history will be recorded on CRFs along with the values of SpCO, SpHb, COHb and hemoglobin concentration. If an abnormal COHb (>10%) value is observed, the measurement will be repeated using a Masimo FDA-cleared pulse CO-oximeter (e.g. Rad-57 and DCI sensor). If abnormal values are confirmed, the patient's clinician will be notified by research staff immediately. The clinician will independently determine any course of action related to patient care utilizing this information. CRFs will be kept within a locked filing cabinet in the Emergency Medicine Research Office which is locked. A de-identified data spread sheet will be created and kept on a storage device with encryption.

Stage 2: We will also approach patients with known CO exposure or who have anemia to enroll them in an arm of this study. Research staff will be notified of any patient presenting to the emergency department with suspected CO exposure or toxicity including patients with signs and symptoms of CO toxicity (headache, nausea, vomiting, rescued from fire, unexplained neurological deficits) or who have low hemoglobin values for any reason determined as part of their routine care. The treating provider will be notified if the patient has agreed to participate and if the clinician determines an IV is necessary, these patients will also be eligible for inclusion in the study.

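### The visible plan does not require the SpHb reading to precede the treatment it is meant to predict, so readings taken after transfusion has started can enter both the derivation and the validation set

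*Combined protocol and SAP*

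**What the plan says.** Section 2 gives the purpose as evaluating triage screening in the emergency department (ED). SpHb primary objective 2a is to "Establish threshold of SpHb that best predicts the clinical outcome of" acute anemia treatment, defined as "blood transfusion, admission to hospital for further workup of anemia, or admission to operating room". No time window or starting point is attached to that outcome.

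Objective 2b derives the threshold by ROC analysis of the "pooled results from the first set of 500 subjects for each institution". Objective 2c is to "Validate the SpHb threshold that predicts the outcome of" the same treatment, "using a second set of subjects of 500 subjects from each institution". Section 5.1 states "At least 3000 subjects across three sites may be enrolled onto this study", about 1000 per site.

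On when subjects are read:

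- Section 5.4 (Subject Recruitment) takes patients "who have received or will receive a blood test for CBC or an IV catheter during their care" and adds that patients who have anemia will be approached.
- Section 7, Stage 1, places the sensor after consent. The only timing link is to the study blood sample, drawn near-simultaneously; the width of that window is blacked out.
- Section 7, Stage 2, seeks patients "who have low hemoglobin values for any reason determined as part of their routine care".
- Section 5.3 has two exclusions, one on consent and one on nails and fingers. Neither concerns transfusion.
- The CRF items listed in sections 7 and 9.4 include no time of reading, transfusion start or treatment order.

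**The concern.** A threshold that predicts an event has to come from measurements made before the event. Here the entry routes let the order reverse. In Stage 2 the clinical hemoglobin result exists before consent and therefore before the sensor is placed. The patients sought this way are also the ones most likely to be transfused or admitted, so late readings would tend to concentrate among the outcome events.

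Two different things can then go wrong. If blood has started, hemoglobin and hence SpHb can rise in an outcome-positive subject, bringing that reading closer to those of subjects without the outcome. If treatment has only been ordered, SpHb is unchanged, but the reading no longer shows that a triage value would have anticipated the decision. The first can distort the cut-off and its accuracy. The second weakens what the cut-off can be claimed to do. The validation step protects against neither, because the second 500 per site come through the same routes.

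**Working it through.** **1. The plan's own figure.** 3 sites × (500 + 500) = 3000, which matches section 5.1. Derivation is 3 × 500 = 1500 and validation is 3 × 500 = 1500. The two sets therefore take up the whole planned enrolment, and no text sets Stage 2 subjects aside. The documents give no event rate, target accuracy or share of late readings, so everything below rests on assumed inputs.

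**2. Direction at a fixed cut-off.** Let a share p of all events be read after a rise r. Then

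sensitivity(c) = (1 − p) Φ((c − μ)/σ) + p Φ((c − μ − r)/σ).

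Specificity does not contain p, so at a fixed cut-off it does not change. Assumed: event hemoglobin mean μ = 7.5 and SD 1.5 g/dL, device error SD 1.0, c = 9. Then σ = √(1.5² + 1.0²) = 1.803.

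- No late readings: Φ(0.832) = 0.797, or 80%.
- p = 10%, r = 1: 0.9 × 0.797 + 0.1 × Φ(0.277) = 0.717 + 0.061 = 0.778, or 78%.
- p = 20%, r = 2: 0.8 × 0.797 + 0.2 × Φ(−0.277) = 0.638 + 0.078 = 0.716, or 72%.
- p = 40%, r = 2: 0.6 × 0.797 + 0.4 × 0.391 = 0.478 + 0.156 = 0.635, or 64%.

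These are severe cases, because p is a share of all events and only transfused events can be shifted. If 60% of events are transfused, p = 40% means that two thirds of them were read late (0.40/0.60). If 30% are transfused, p = 40% cannot occur.

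**3. Re-optimised cut-off, shifting transfused cases only.** Simulated derivation sets of 1500, 200 replicates per scenario, cut-off chosen by the Youden index (the plan names no criterion). Assumed: outcome prevalence 5% or 10%; hemoglobin mean 8.0 (SD 1.5) with the outcome and 13.0 (SD 1.8) without; device error SD 1.0; 30% or 60% of events transfused; a share f of those read late. Ranges are over the four combinations of prevalence and transfused share.

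| f and rise | Cut-off, g/dL | Shift against the matching f = 0 run | Apparent sensitivity | Specificity | AUC |
|---|---|---|---|---|---|
| 0 | 10.36-10.43 | – | 0.917-0.928 | 0.893-0.901 | 0.966-0.967 |
| 10%, 2 g/dL | 10.40-10.47 | −0.02 to 0.11 | 0.908-0.917 | 0.889-0.894 | 0.959-0.963 |
| 25%, 2 g/dL | 10.45-10.55 | 0.02 to 0.20 | 0.888-0.910 | 0.883-0.891 | 0.951-0.958 |
| 50%, 2 g/dL | 10.53-10.76 | 0.11 to 0.40 | 0.867-0.898 | 0.861-0.882 | 0.935-0.952 |
| 100%, 3 g/dL (extreme) | 10.81-11.36 | 0.38 to 0.99 | 0.752-0.822 | 0.781-0.855 | 0.845-0.907 |

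The four f = 0 runs differ among themselves by 0.07 g/dL (10.425 − 10.358), so the shift in the 10% row is hardly distinguishable from simulation noise.

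**4. What the shifted cut-off would do in use.** In the 50%, 2 g/dL row, applying the shifted cut-off to the same events' pre-transfusion values gives sensitivity 0.930-0.941, against the apparent 0.867-0.898. The study would understate sensitivity at its own cut-off, and the higher cut-off would cost specificity.

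**The case against.** The best defence is that the text shows late readings to be possible, not frequent. Having had a CBC is neither treatment nor a decision to treat, and section 5.4 covers patients before as well as after it. Stage 2 eligibility depends on the clinician judging an IV necessary, which suggests enrolment at or before that step. The plan calls Stage 2 an arm and does not say that it feeds the 500 + 500 sets; enrolment of at least 3000 leaves room for subjects outside them. The CRF list in section 9.4 is not exhaustive, and device data are uploaded under section 9.5, so times may exist. Section 4 is not in the text available for review, and a timing rule there cannot be ruled out.

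Most of this stands as a limit on size and certainty. It does not supply the missing rule. The IV condition governs eligibility, not the order of reading and treatment. Nothing visible keeps Stage 2 subjects out of the ROC sets. Even if times are captured, no analysis rule uses them.

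A reader might infer something stronger: that the threshold is not a prediction at all, that it is biased by transfusion, or that a typical Stage 2 patient already has blood running. The documents support none of these. They give no share of late readings, readings taken before treatment remain predictive, and of the three outcome components only transfusion raises hemoglobin before an ED reading. An order or a disposition does not move SpHb.

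It can also be objected that dropping everyone with a prior order would remove subjects whose SpHb is unaffected, possibly the most severe cases. That is a fair point, and it argues for making that exclusion a sensitivity analysis only.

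**Conclusion.** The point holds as a gap in the analysis rule with a possible bias of unknown size. As written, the plan would let readings taken after transfusion started in outcome-positive subjects count in both derivation and validation. The effect would be an upward shift of the cut-off and lower apparent accuracy.

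If few transfused cases are read late, the effect is negligible. If about half are, with a 2 g/dL rise, the cut-off moves by a few tenths of a gram and apparent sensitivity falls by about 3 to 5 percentage points (0.928 − 0.898 = 0.030 up to 0.925 − 0.873 = 0.052). These sizes rest on the assumed hemoglobin distributions, device error, transfused share and Youden criterion. The direction needs only that transfusion raises the reading. Readings after an order but before blood starts are a separate and weaker matter: they bear on the triage claim, not on the value of the cut-off. This is a cheap improvement, not a flaw that invalidates the objective.

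**What to change.** Record on the CRF the time of the SpHb reading, the time any transfusion started, and the time of any order for transfusion, anemia admission or the operating room. The device may supply the first and the chart the others.

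State before analysis that for objectives 2a-2c:

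- the primary ROC and validation sets contain only readings taken before any transfusion starts and before arrival in the operating room;
- later readings are reported separately, with their number by site and by stage;
- sensitivity analyses (i) also exclude readings taken after an order and (ii) include all readings.

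The cost is a few extra times per subject and the loss of some outcome events, mainly from Stage 2. Patient care does not change, and the rule does not by itself alter the planned 3000. The times should be collected prospectively, because without them late readings may not be separable afterwards.

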
The device manufacturer has developed a new diagnostic platform that allows for simultaneous measurement of SpO2, SpCO and SpHb, with modifications that may improve diagnostic performance. Most emergency department routinely measure SpO2 during triage, and some (such as Rhode Island Hospital) also measure SpCO. Enhancement of the triage oxyhemoglobin profile to include total Sp CO and SpHb could provide significant benefit in a busy emergency department setting.

Determination of anemia rapidly in the Emergency Department may prevent morbidity and mortality. Patients with traumatic injuries causing hemorrhage, occult internal hemorrhage (GI bleeding, ectopic pregnancy, etc.), hemolysis, or other critical anemias, could be quickly identified. Triage nurses could then expedite physician evaluation and acquisition of blood samples for type and cross. Screening for anemia is subjectively performed by observing for pallor in the skin and mucous membranes (in particular, the palpebral conjunctiva). However, studies have shown that this method is not reliable. Validation of a non-invasive screening method that may be utilized in the pre-hospital setting or in emergency department triage could prevent complications associated with delays in diagnosis of anemia by blood analysis.

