#### 5.2 Inclusion Criteria

- Age 1 year or older.
- At least one digit has acceptable width as measured by study-provided digit gauge.
- Presenting to emergency department for any complaint.
- Potential for IV catheter and/or blood draw for CBC as standard of care.

---

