### 5.3 Exclusion Criteria

- Patients who are unable to consent and also surrogate consent was unable to be obtained.
- Patients with fingernail polish, discoloration or trauma to fingers.

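### As written, objective 2a counts any operating-room admission as acute treatment of anemia, so unrelated surgery is an outcome event in both deriving and validating the SpHb threshold

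*Combined protocol and SAP*

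**What the plan says.** Section 2, SpHb primary objective 2a, seeks the SpHb threshold that best predicts acute treatment of anemia, and defines that outcome as "blood transfusion, admission to hospital for further workup of anemia, or admission to operating room". The second item carries its own anemia qualifier. The third has no indication attached.

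The same outcome is used twice. Objective 2b sets the threshold by "receiver operating curve analysis of the pooled results from the first set of 500 subjects for each institution", and objective 2c validates it "using a second set of subjects of 500 subjects from each institution".

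The population is broad. Section 5.2 admits patients "Presenting to emergency department for any complaint". Section 5.3 has two exclusions: inability to obtain consent from the patient or a surrogate, and "Patients with fingernail polish, discoloration or trauma to fingers". Neither is directed at surgical presentations.

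Two passages bear on intent and case mix. In Section 1.1 the rationale is that "Patients with traumatic injuries causing hemorrhage, occult internal hemorrhage (GI bleeding, ectopic pregnancy, etc.), hemolysis, or other critical anemias, could be quickly identified". Section 5.4 adds targeted recruitment: "We will also approach patients with known CO exposure or who have anemia to enroll them in this study".

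**The concern.** The outcome is whatever the list says it is, and the list includes every operating-room admission. An appendectomy or a fracture repair in a patient with normal hemoglobin would count as acute treatment of anemia. SpHb would then be charged with missing anemia treatment in a patient who received none.

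This is the target of a primary objective. Because derivation and validation use the same definition, the second set would reproduce the problem and not expose it. If staff at the three sites instead infer that surgery for blood loss was meant, they may code the same operation differently, since the text gives them no rule.

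**Working it through.** **Design figures from the documents.** Three sites at about 1,000 each (Section 5.1) give 3 × 1,000 = 3,000. This agrees with objectives 2b and 2c: 3 × (500 + 500) = 3,000, or 1,500 subjects in each set. The plan states no event rate, AUC, target sensitivity or precision for objective 2, so there is no planned performance figure to reproduce.

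**Assumptions (none is from the documents).**
- SpHb in SD units: non-events N(0,1), true anemia events N(−d,1), true AUC 0.90. So d = √2 × z(0.90) = 1.812.
- Cut-off at specificity 0.80, that is −0.842. True sensitivity = Φ(−0.842 + 1.812) = 0.834.
- p = share of all subjects with true anemia events; q = share with unrelated operating-room admission; w = q/(p + q), the unrelated share of events.
- In the base case unrelated surgery is independent of hemoglobin, so a fraction 0.20 of these patients fall below the cut-off and their AUC against non-events is 0.50.

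**Formulas.**
- Observed sensitivity = (1 − w) × 0.834 + w × 0.20
- Observed AUC = (1 − w) × 0.90 + w × 0.50

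Example, p = 5% and q = 1%: w = 1/6 = 0.167. Sensitivity = 0.833 × 0.834 + 0.167 × 0.20 = 0.728. AUC = 0.833 × 0.90 + 0.167 × 0.50 = 0.833.

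| p | q = 0.5%: sens / AUC | q = 1%: sens / AUC | q = 2%: sens / AUC |
|---|---|---|---|
| 2% | 0.71 / 0.82 | 0.62 / 0.77 | 0.52 / 0.70 |
| 5% | 0.78 / 0.86 | 0.73 / 0.83 | 0.65 / 0.79 |
| 10% | 0.80 / 0.88 | 0.78 / 0.86 | 0.73 / 0.83 |

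**How much contamination matters.** The loss in sensitivity is w × (0.834 − 0.20) = 0.634w. Five points need w = 0.079, one unrelated operation per 11.7 anemia events. Ten points need w = 0.158, one per 5.3.

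**Relaxing independence.** If unrelated surgical patients have lower hemoglobin than non-events (AUC 0.70 against them), 0.46 of them fall below the cut-off. At p = 5%, q = 1% or 2% gives sensitivity 0.77 or 0.73 and AUC 0.87 or 0.84.

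**Effect on the threshold, p = 5%.**
- *Youden.* Under independence the index is multiplied by (1 − w) at every cut-off, so its maximum stays at −d/2 = −0.906 (specificity 0.818). Observed sensitivity there falls from 0.818 to 0.712 (q = 1%) or 0.636 (q = 2%). In a simulation with 1,500 subjects per set and 2,000 replicates, the median Youden cut-off moved by at most 0.06 SD across p = 2% to 10% and q = 0 to 2%.
- *90% sensitivity.* The cut-off moves from −0.531 to 0.100 (q = 1%) or 0.464 (q = 2%), a rise of 0.63 or 1.00 SD. Specificity falls from 0.70 to 0.46 or 0.32, while sensitivity for true events rises to 0.97 or 0.99. If surgical patients have lower hemoglobin (AUC 0.70), specificity falls to 0.60 or 0.53.

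**A second parameterisation.** With assumed SpHb means of 9 and 13 g/dL and SD 1.8, p = 2% and q = 1% (30 and 15 events in 1,500), AUC goes from 0.94 to 0.80 and Youden sensitivity from 0.87 to 0.62. The cut-off stays at 11.0 g/dL.

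**The case against.** **Intent.** The list defines an outcome named for the treatment of anemia, and Section 1.1 speaks of hemorrhage, GI bleeding and ectopic pregnancy. A sensible abstractor might leave out unrelated surgery. The intent is probably right, but the outcome is expressly defined by the list, and the drafters qualified one item and not the other. The intent does not amend the rule.

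**Cut-off rule.** Asking for the threshold that predicts best points towards an optimising criterion such as Youden, under which the cut-off hardly moves. The fixed-sensitivity figures rest on a rule that the plan does not state. This is fair: they show only what happens if such a rule is chosen. The plan names no criterion, and the loss of sensitivity and AUC occurs under either.

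**Direction and estimand.** If any operating-room admission really is the outcome, nothing is biased; and relative to anemia treatment the error makes the device look worse, not better. Both points are correct. The bias is relative to the outcome that the label names, which is the one the objective is about.

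**Size.** Every rate is assumed, and active recruitment of anemic patients dilutes the effect. At 10% anemia events and 0.5% unrelated surgery, sensitivity falls by only 3 points (0.83 to 0.80). A small effect is not excluded.

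**Unseen material.** The text between Sections 3 and 5, the CRF itself and the clinician survey were not available, and the CRF contents listed in Section 9.4 are expressly not exhaustive. A field or rule may exist there. A field alone would not help unless a rule also narrows the definition.

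**Reach.** SpHb primary objective 1, the agreement objective and all SpCO objectives do not use this outcome.

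**Conclusion.** The concern holds. On the text supplied, unrelated operating-room admission is an event in the outcome for a primary objective, in both the derivation and the validation set. The wording defect is certain; its numerical effect is not, because the documents give no event rates.

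Under the assumed model, with anemia events at 2% to 10% and unrelated surgery at 0.5% to 2%, the loss of sensitivity runs from about 3 to 32 points and the loss of AUC from about 0.02 to 0.20. The losses are smaller if surgical patients tend to have lower hemoglobin. The threshold is nearly unaffected under Youden and can move materially under a fixed-sensitivity rule. The point should be fixed before the outcome is abstracted.

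**What to change.** In objective 2a, replace the operating-room item with admission to the operating room with bleeding or anemia as the indication. Take the indication from the operative or admitting diagnosis in the chart, under one short written rule common to all sites. Existing staff can abstract it, without reference to SpHb and, where practicable, without the laboratory hemoglobin. Report the any-cause version as a sensitivity analysis: it errs low, the attributed version may err high, and the two together show how much the definition matters.

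The cost is one phrase, a short abstraction rule and, if the indication is not already captured, one CRF field. There are two downsides.

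- **Fewer events, wider intervals.** With 1,500 validation subjects and true events in 2%, 5% or 10% (assumed), there are 30, 75 or 150 events. The 95% Wilson interval around a sensitivity of 0.83 is then 0.66–0.93, 0.73–0.90 or 0.76–0.88.
- **Subjective attribution.** Section 7 puts the predictor and the reference on the same form: "smoking history will be recorded on CRFs along with the values of SpCO, SpHb, COHb and hemoglobin concentration". It also says that Stage 1 data will be unmasked at the end, but the supplied text does not say from whom SpHb is masked. An abstractor who knows the hemoglobin could build it into the outcome. As an assumed worst case, every low-hemoglobin operation is counted and every high one dropped. With s the share of true events that qualify only through the operating room, observed sensitivity = (p × 0.834 + q × 0.20) / (p × (1 − 0.166s) + q × 0.20). At p = 5% and q = 1% this gives 0.87 for s = 20% and 0.91 for s = 50%, against a true 0.83. This is why the rule should rest on the charted diagnosis and the any-cause analysis should be kept.
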